Appendix 1.2. Evaluation of Best Overall Response

The best overall response (BOR) is the best response recorded from start date until disease progression or start of new anti-cancer therapy. BOR is determined by the following order.

CR: One objective status of CR documented before progression and start of new anti-cancer therapy.

PR: One objective status of PR documented before progression and start of new anti-cancer therapy, but not qualifying as CR.

SD: At least one objective status of SD documented at least (8 weeks -1 days) after start date and before progression and the start of new anti-cancer therapy but not qualifying as CR or PR.

PD: Progression documented within (16 weeks + 1 days) after start date and not qualifying as uCR, uPR, or SD.

NE: All other cases. Note that reasons for NE should be summarized and the following reasons could be used:

- Early death (*Note: death prior to (8 weeks 1 days) after start date*)
- No post-baseline assessments
- All post-baseline assessments have overall response of NE
- New anti-cancer therapy started before first post-baseline assessment
- SD too early (< (8 weeks 1 days) after start date)
- PD too late (> (16 weeks + 1 days) after start date)

Special and rare cases where BOR is NE due to both early SD and late PD will be classified as 'SD too early'.

Appendix 1.3. Censoring for Time to Event Data

Table A.1.3.1 summarizes the censoring rules for the PFS analysis and displays censoring hierarchy for this study. Table A.1.3.2 shows the general reasons for PFS censoring and where the censoring hierarchy in Table A.1.3.1 came from.

Table A.1.3.1 PFS Censoring Reasons and Hierarchy

Censoring Hierarchy	Situation	Date of Event or Censor	Event / Censor
1	No baseline radiological tumor assessment available	Date of First Dose	Censored
2	New anticancer treatment started and no tumor progression	Date of previous adequate radiological assessment immediately prior to start of new therapy	Censored
3	Tumor progression (per RECIST 1.1) documented after 2 scan intervals following previous adequate radiological tumor assessment	Date of previous adequate radiological assessment	Censored
4, 5	No tumor progression (per RECIST 1.1) and patient lost to follow-up or withdrawal of consent	Date of last adequate radiological Assessment	Censored
6	No post baseline radiological tumor assessment available and no death reported within 2 scan intervals following the date of the first dose of study drug (napabucasin)	Date of First Dose	Censored
	No post baseline radiological tumor assessment available but death reported within 2 scan intervals following the date of the first dose of study drug (napabucasin)	Date of Death	Event
7	No tumor progression (per RECIST 1.1) and no death reported within 2 scan intervals following last adequate radiological tumor assessment	Date of last adequate radiological tumor assessment	Censored
	No tumor progression (per RECIST 1.1) but death reported within 2 scan intervals	Date of death	Event

following last adequate radiological tumor assessment		
Tumor progression (per RECIST 1.1) documented within 2 scan intervals following previous adequate radiological tumor assessment	Earliest of the target, non- target and new tumor assessment dates	Event

Notes: (1) Symptomatic deteriorations (ie, symptomatic progressions, which are not radiographically confirmed) will not be considered as progressions.

(2) If target, non-target and new lesion assessments have different dates within a visit, then the earliest of those dates will be considered as the date of the tumor assessment if the assessment for that visit is progressive disease (PD); otherwise the latest date will be used.

(3) Adequate radiographical tumor assessment refers to an assessment with overall response of CR, PR, SD, or PD.

Table A.1.3.2 PFS Censoring Reasons and Hierarchy

Hierarchy	Condition	Censoring Reason
1	No adequate baseline assessment	No adequate baseline assessment
2	Start of new anti-cancer therapy before event.	Start of new anti-cancer therapy
3	Event more than (16 weeks+1 day) from last adequate post- baseline tumor assessment/start date	Event after missing assessments ^a
4	No event and [withdrawal of consent date ≥ start date OR End of study (EOS) = Patient refused further FU]	Withdrawal of consent
5	No event and lost to follow-up in any disposition page	Lost to follow-up
6	No event and [EOS present OR disposition page for any EPOCH after screening says patient will not continue into any subsequent phase of the study] and no adequate post- baseline tumor assessment	No adequate post-baseline tumor assessment
7	No event and none of the conditions in the prior hierarchy are met	Ongoing without an event

^a More than (16 weeks+1 day) after last adequate tumor assessment. *Note: This should correspond to 2 or more missing assessments using the nominal schedule of assessments but best to describe directly as 16 weeks to match on how the analyses are performed as per the table above>*

Date of Last Contact for Overall Survival

The date of last contact will be derived for patients not known to have died at the analysis data cutoff date using the latest complete date (non-imputed) among the following:

• All patient assessment dates (eg, blood draws [laboratory, PK], vital signs, performance status, ECG, tumor assessments, concomitant radiation, surgery)

- Start and end dates of follow-up anti-cancer therapies
- AE start and end dates
- Last date of contact where "Patient Remains in Follow-up" collected on the "Survival Follow-up" eCRF (do not use date of survival follow-up assessment unless status is alive)
- Study drug start and end dates
- Randomization/enrollment date
- Date of discontinuation on disposition eCRF pages (do not use if reason for discontinuation is lost to follow-up or death).

Note:

- Only dates associated with patient visits or actual examinations of the patient should be used. Dates associated with a technical operation unrelated to patient status (eg, the date a blood sample was processed) should not be used.
- Assessment dates after the cutoff date will not be applied to derive the last contact date.

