3.2. Secondary Endpoints

- PK parameters of napabucasin administered in combination with cetuximab, or panitumumab, or capecitabine.
- PK parameters of capecitabine and metabolite (5-FU).
- Pharmacodynamics parameters (or biomarkers) of napabucasin administered in combination with cetuximab, or panitumumab, or capecitabine. Response (increase or decrease) of several biomarkers of napabucasin from biopsied tumors following napabucasin administration will be examined in patients with accessible tumors who consent to an optional biopsy.
- Objective Response Rate (ORR)

ORR is defined as the percentage of patients with a best overall response (BOR) of complete response (CR) or partial response (PR). The categorizations of response (CR, PR, SD, PD, and NE) and the derivations of BOR is provided in Appendix 1.1 and 1.2.

• Progression Free Survival (PFS) and Overall Survival (OS)

PFS is defined as the time from the date of first treatment (or date of enrollment in sensitivity analysis) to the date of first documentation of progressive disease (PD) or death due to any cause, whichever occurs first.

OS is defined as the time from the date of treatment (or date of enrollment in sensitivity analysis) to the date of death. Patients without documentation of death at the time of analysis will be censored at the date last known to be alive.

• Dose Limiting Toxicities (DLTs): For definition of DLT, see Section 4.5 of the protocol amendment 2 [5].

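### SAP Table A.1.3.1 censors PFS when a patient withdraws or is lost and then dies within two scan intervals, unlike its stated source table and the PFS definition; its new-therapy row also omits the timing

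*SAP*

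**What the plan says.** **PFS definition.** SAP Section 3.2 runs PFS "to the date of first documentation of progressive disease (PD) or death due to any cause, whichever occurs first".

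**Which table governs.** The overview table in SAP Section 8.2.3.3 sends PFS censoring to Table A.1.3.1. The lead-in to Appendix 1.3 says that A.1.3.1 summarizes the PFS rules, and that A.1.3.2 shows the general reasons and is where the A.1.3.1 hierarchy came from.

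**Withdrawal and loss to follow-up.**
- A.1.3.1 rows 4,5: "No tumor progression (per RECIST 1.1) and patient lost to follow-up or withdrawal of consent". Censored at the last adequate scan.
- A.1.3.1, death line under row 7: "No tumor progression (per RECIST 1.1) but death reported within 2 scan intervals" of the last adequate scan. Event at the date of death.
- A.1.3.2 row 4: "No event and [withdrawal of consent date ≥ start date OR End of study (EOS) = Patient refused further FU".
- A.1.3.2 row 5: "No event and lost to follow-up in any disposition page".

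**New therapy.**
- A.1.3.1 row 2: "New anticancer treatment started and no tumor progression". Censored at the adequate scan just before the new therapy.
- A.1.3.1, last line: progression "documented within 2 scan intervals following previous adequate radiological tumor assessment" is an event. No exception is made for new therapy already started.
- A.1.3.2 row 2: "Start of new anti-cancer therapy before event".

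**General rule.** SAP Section 7.4 censors time-to-event endpoints for patients who withdraw, drop out or are lost before progression or death is documented, and refers to Appendix 1.3 for PFS.

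**The concern.** One table is said to come from the other, yet the conditions differ. A.1.3.1 rows 4,5 test for progression only. A.1.3.2 rows 4 and 5 test for any event, which under Section 3.2 includes death.

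The difference falls on patients who leave follow-up and die soon afterwards. They are likely to be among the sicker patients, so censoring them at their last scan is informative: known deaths leave the event count and the Kaplan-Meier curve rises. The study is non-randomized and PFS is not tested, so that curve is itself the PFS result.

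The new-therapy row raises a lesser question. It does not say whether the absence of progression is judged when the new therapy starts or at any later time. If it means at any time, progression after a switch counts as an event.

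**Working it through.** **1. Inputs.** Scans are 8 weeks apart (Protocol Section 5.4), so two scan intervals are 2 × 8 × 7 = 112 days. A.1.3.2 uses 16 weeks + 1 day, or 113 days. An event is PD or death (SAP Section 3.2).

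**2. Both tables applied in rank order.** The last adequate non-PD scan is on day 56. A.1.3.2 has no event column, so an event there means that no censoring row applies.

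| History | Days from scan | A.1.3.1 | A.1.3.2 with Section 3.2 |
|---|---|---|---|
| Withdrawal or loss day 70, death day 112, no PD | 56 | Censored (rows 4,5) | **Event** |
| Withdrawal or loss day 70, death day 200, no PD | 144 | Censored (rows 4,5) | Censored (row 3) |
| Withdrawal or loss day 70, alive | – | Censored (rows 4,5) | Censored (rows 4, 5) |
| Withdrawal or loss day 70, PD recorded day 112 | 56 | Event | Event |
| No withdrawal, death day 112, no PD | 56 | Event | Event |
| New therapy day 70, PD day 112 | 56 | **Event** if row 2 is read literally | Censored (row 2) |
| New therapy day 70, PD day 200 | 144 | Censored (row 3) | Censored (row 2) |
| New therapy day 70, death day 112, no PD | 56 | Censored (row 2) | Censored (row 2) |

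Two histories disagree, in opposite directions, and only when the event lies inside the window. There is also a one-day edge: an event exactly 113 days after the scan is outside the A.1.3.1 window and inside the A.1.3.2 window.

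**3. Patients with no post-baseline scan.** Rows 4,5 date the censoring at the last adequate assessment. Note 3 to A.1.3.1 defines adequate as having an overall response of CR, PR, SD or PD, which a baseline scan does not have, so rows 4,5 supply no date. Row 6 describes these patients and makes death within two intervals of first dose an event. By rank, rows 4,5 come first; by content, row 6 fits. The table does not settle it.

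**4. Size for withdrawal or loss followed by death.** The plan has no figure to reproduce. The simulation assumed 50 patients (the approximate number per arm in SAP Section 4.3), exponential progression times with median 13 weeks (the phase I colorectal PFS in Protocol Section 1.4), 8-weekly scans, withdrawal between weeks 2 and 16, a median of 8 weeks from withdrawal to death, and all deaths known. Both rules were applied to the same patients in 1,500 trials, in strict rank order.

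| Withdrawing | Mean events, A.1.3.1 vs A.1.3.2 | Mean median PFS (weeks) | Difference (weeks) |
|---|---|---|---|
| 10% | 46.1 vs 48.5 | 17.1 vs 16.5 | 0.6 |
| 20% | 41.9 vs 47.0 | 17.2 vs 16.0 | 1.2 |
| 30% | 38.0 vs 45.5 | 17.2 vs 15.6 | 1.6 |

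Repeat runs gave 0.4–0.7 weeks for 5–10% withdrawal, 17.3 − 16.0 = 1.3 at 20%, and 17.2 − 15.5 = 1.7 at 30%. At 20%, 16-week PFS was about 43% vs 40%.

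If row 6 governs patients with no post-baseline scan, A.1.3.1 at 20% gives 44.6 events and a median of 16.5 weeks. The event gap falls from 47.0 − 42.1 = 4.9 to 47.0 − 44.6 = 2.4, the median gap from 1.3 to 16.5 − 16.0 = 0.5 weeks, and 16-week PFS is 40% under both. The trial-to-trial SD of the median was about 2.4–3.4 weeks.

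**5. Size for new therapy.** None is given. It depends on how many patients switch before PD and are still scanned afterwards, which the documents do not state.

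**The case against.** **A.1.3.1 is the operative table.** A reader might infer that PFS event status simply depends on which table the programmer picks. The documents do not support that: Section 8.2.3.3 names A.1.3.1, and A.1.3.2 has neither a date column nor an event column. This stands and narrows the point. What remains is that the operative table departs from its stated source and from Section 3.2.

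**Section 7.4 can be read as agreeing with rows 4,5.** Withdrawal before a documented death leads to censoring. This stands in part, and it means that editing the appendix alone would leave a conflict with Section 7.4. But that section defers to Appendix 1.3 for PFS. Read literally it would also censor OS for a death known after withdrawal, whereas Section 3.2 censors OS only where no death is documented. It does not settle what was intended.

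**Row 2 naturally means no progression before the new therapy.** A reader might infer that A.1.3.1 charges progression on a later drug to BBI608. That follows only from the most literal reading. The row's censoring date is the scan just before the switch, SAP Section 7.1 imputes new-therapy dates in order to set censoring dates, and Appendix 1.2 ends best overall response at new therapy. All of this suggests that censoring is intended. On that reading the tables agree, and what is left is an omission in the wording.

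**The rates are assumed.** This stands. The documents give no withdrawal rate and no time from withdrawal to death. That every death is known is generous, because deaths after withdrawal or loss may not be recorded, and the effect shrinks as fewer are.

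**Conclusion.** The mismatch is real and confined to a few cells. The main case is the patient with at least one adequate post-baseline scan who withdraws or is lost and is known to have died within two scan intervals without RECIST PD: censored under A.1.3.1, but an event under Section 3.2, with no censoring row in A.1.3.2 that applies. Following A.1.3.1 lengthens PFS. For patients with no post-baseline scan, rows 4,5 and row 6 overlap and the order needs stating. The new-therapy row is a secondary point of unclear wording.

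The size cannot be computed from the documents. Under the assumptions above, the shift in median PFS is about 0.4–1.7 weeks for 5–30% withdrawal on strict rank order, and about 0.5 rather than 1.3 weeks at 20% if row 6 governs patients without a post-baseline scan. That is small beside the sampling variation of the median, but its direction is systematic.

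A reader might go on to infer that the trial's conclusions are at risk. They are not: PFS is secondary and descriptive, SAP Section 4.1 plans no hypothesis test, and neither DCR nor any decision rule uses these tables. Severity is minor to moderate.

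**What to change.** Before the PFS derivation is run:

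1. **A.1.3.1 row 2:** reword to *New anticancer treatment started before documented progression or death*.
2. **A.1.3.1 rows 4,5:** add *and no death within 2 scan intervals of the last adequate assessment (or of first dose if there is no post-baseline assessment)*. State whether row 6 takes precedence over rows 4,5 when there is no post-baseline scan.
3. **Section 7.4:** reword so that, for PFS, a known death inside the window counts as an event even after withdrawal or loss to follow-up.

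If the sponsor does intend to censor such deaths, A.1.3.2 rows 4 and 5 and the PFS definition in Section 3.2 should say so instead.

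The cost is two table cells, a note on precedence and one sentence in the SAP. No new data are needed.

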### **5.4** Tumor Evaluation Visits

Disease status and tumor response will be assessed in eight-week intervals up to one year after starting therapy (calculated from the first dose of BBI608) or as clinically indicated. Standard

imaging studies should be performed according to institutional procedures. Tumor response for solid tumors will be evaluated using the guidelines for Response Evaluation Criteria in Solid Tumors (RECIST 1.1) outlined in Section 9.

Once progression of disease during therapy is documented, patients must be taken off treatment and may receive any therapy as determined by their treating physician.

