## 5.6 Discontinuation from Study

Patients will be removed from the study at any time if they meet any of the following criteria:

- Documented radiologic or clinical progression of disease
- Noncompliance with any part of the study, as evaluated by the Principal Investigator and Medical Monitor
- Withdrawal of consent
- Lost to Follow-up
- Death
- Clinically unacceptable toxicities despite optimal treatment.

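### Clinical progression without scan confirmation takes patients off study but is censored in PFS, and no planned analysis shows how much this raises the estimate

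*SAP*

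**What the plan says.** Protocol 5.6 lists among the reasons for removal from study "Documented radiologic or clinical progression of disease". The SAP's study design section likewise ends treatment cycles for progression of either kind. Scans run on a fixed schedule (Protocol 5.4): "Disease status and tumor response will be assessed in eight-week intervals up to one year after starting therapy". The synopsis limits these evaluations to the time patients remain on study.

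Note 1 to SAP Table A.1.3.1 states: "Symptomatic deteriorations (ie, symptomatic progressions, which are not radiographically confirmed) will not be considered as progressions". Depending on what else happened, a patient who leaves for unconfirmed clinical progression falls under one of these rows:

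- Row 2, "New anticancer treatment started and no tumor progression": censored at the adequate scan before the new therapy. This row ranks above the rows that count deaths.
- Row 6, "No post baseline radiological tumor assessment available and no death reported within 2 scan intervals": censored at the date of first dose.
- Row 7, "No tumor progression (per RECIST 1.1) and no death reported within 2 scan intervals following last adequate radiological tumor assessment": censored at that last scan.

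The second parts of rows 6 and 7 make an early death an event. For row 6 the condition is "No post baseline radiological tumor assessment available but death reported within 2 scan intervals", and row 7 does the same counting from the last adequate scan.

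SAP 8.2.3.3 plans one Kaplan-Meier PFS analysis, in the safety set from first treatment. It adds that a sensitivity analysis in the full analysis set, counted from enrolment, may be considered.

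**The concern.** Kaplan-Meier assumes that a patient censored at a given time has the same outlook as those still followed. A patient taken off study for clinical progression does not. The rule also backdates the censoring to the last scan, or to first dose, which is before the deterioration. The first on-study scan is due at about week 8, and Protocol 4.6 expects most patients to be treated for only 4 to 16 weeks, so exits before any post-baseline scan are foreseeable.

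The outputs would not reveal it. In SAP Table A.1.3.2 no censoring reason names clinical progression. A clinical progressor with an earlier scan, no new therapy, no withdrawal of consent and no loss to follow-up drops to the last category, which labels the patient as ongoing.

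The study has no control arm, so any reader who wants to interpret PFS must set it against outside values. Protocol 1.4 does this for the phase I data (13 weeks against 7.7 weeks). A PFS estimate that is too high would flatter such a comparison.

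**Working it through.** **Stated figures.** The documents give no PFS target, event count or expected censoring share, so there is no PFS result to reproduce. One internal check is possible: two scan intervals = 2 x 8 = 16 weeks. This agrees with the footnote to Table A.1.3.2, "More than (16 weeks+1 day) after last adequate tumor assessment".

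**Direction.** Take as reference an analysis that counts clinical progression as an event on its date. At a scheduled scan date, every clinical progressor censored before that date under the SAP rule has already failed in the reference, or has failed by that same date. Censoring passes that patient's weight to patients still at risk, some of whom survive, and a counted death comes later than the clinical progression. So at scan dates the SAP estimate is equal to or above the reference. Between scans the two curves can cross slightly.

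**Inputs from the documents.** Scans every 8 weeks; median PFS 7.7 or 13 weeks (Protocol 1.4), used for illustration only.

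**Inputs assumed, because the documents do not give them.**
- Exponential PFS.
- Share of progressions that are clinical first, f: 10-40%.
- Share of those with an exit scan showing RECIST progression: 0%, 50% or 100%.
- Median time from progression to death: 12 or 26 weeks.
- 30% of clinical progressors start new therapy.

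**Hand check (no deaths, no new therapy, no confirming scans).** Let p be the probability of progressing within one 8-week interval. A share f of those patients is censored at the start of the interval. The estimated survival per interval is then (1 - p)/(1 - pf), and over 16 weeks it is that value squared. For median 13 weeks and f = 30%:
- 1 - p = 2^(-8/13) = 0.653, so p = 0.347.
- Reference 16-week PFS = 0.653² = 42.6%.
- SAP rule: 1 - pf = 1 - 0.104 = 0.896; 0.653/0.896 = 0.729; 0.729² = 53.1%.
- Overstatement about 10.5 points.

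**Simulation with the death and new-therapy rows applied** (6,000 patients per scenario, noise about 1 point). For the same case it gives 51% against 42-44%, so counting early deaths as events cuts the overstatement to 7-9 points. Across all scenarios:

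| Exit scans confirming progression | Patients censored by this rule | Censored at first dose | 16-week PFS overstated by |
|---|---|---|---|
| None | 6-32% | 2-16% | 2-12 points |
| Half | 3-16% | 1-7% | 1-6 points |
| All | 0% | 0% | 0 points |

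The reference 16-week PFS is about 22-24% for a median of 7.7 weeks and 42-44% for 13 weeks. No scenario lowered the 16-week estimate.

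**Median.** SAP 8.1.1 reports medians, and these can jump by a whole scan interval. With no confirming scans and a true median of 7.7 weeks, the Kaplan-Meier median moved from 8 to 16 weeks at every assumed share, because true 8-week PFS (2^(-8/7.7) = 48.7%) lies just under 50%. With a true median of 13 weeks it moved from 16 to between 16 and 24 weeks.

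**The case against.** A reader might infer that every clinical progressor is censored and that PFS is therefore certain to read too high. The documents do not support that. The end-of-study visit in Protocol 5.5 includes tumor measurement, and a scan there that shows RECIST progression within 16 weeks of the previous adequate scan is an event. Death within 16 weeks is also an event unless a higher censoring row applies. With full confirmation the bias is nil. The safeguard is incomplete, however. The Appendix A schedules waive the exit scan if CT or MRI was done in the previous four weeks, so a patient who declines soon after a stable scan may have none.

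A reader might also infer that the SAP departs from the protocol. On what counts as progression it does not: Protocol 10.4 also ties PFS to RECIST.

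Nor do the documents make PFS a decision endpoint. It is secondary, SAP 4.1 states that nothing is tested, and the historical benchmarks set for this trial are for disease control rate. No error rate is affected, and overall survival does not depend on this rule.

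Finally, the eCRF is not among the documents, and Protocol 5.6 lists radiologic and clinical progression as a single criterion. The two may not be recorded separately, and the fix has to allow for that.

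All of this limits the reach and size of the point. None of it supplies an analysis that would show whether the effect is trivial or material.

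**Conclusion.** The point holds as a robustness gap. Unconfirmed clinical progression is informatively censored, in some cases at first dose, and the effect on PFS at the scan dates is upward or nil. The optional sensitivity analysis changes only the population and the start date, so nothing planned tests the rule.

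The size cannot be known from the documents. The range of 0 to about 12 points on 16-week PFS rests on the assumed 10-40% share of clinical-first progressors and on the assumed scan confirmation, survival and new-therapy rates. The upper end needs both a 40% share and no confirming exit scans. This is a worthwhile, low-cost improvement to a descriptive secondary analysis. It does not invalidate the planned one.

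**What to change.** Keep the current rule for the main PFS analysis and add two items to SAP 8.2.3.3.

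1. A pre-specified sensitivity PFS for each arm, with event = the earliest of RECIST progression, discontinuation for clinical progression (at the discontinuation date), or death from any cause. If the eCRF does not separate clinical from radiologic progression, use discontinuation for progression of either kind.
2. A table by arm of PFS censoring reason against reason for discontinuation, including the number censored at first dose.

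The cost is about one extra Kaplan-Meier table per arm and one cross-tabulation, after checking how the eCRF records the discontinuation reason and its date. The downside is small: clinical progression is judged by the investigator in an open-label study, so this version should stay a sensitivity analysis. If the two PFS estimates agree, the issue is closed. If they differ, the table shows how many patients account for the gap.

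### SAP Appendix 1.3 gives two conflicting rules for the OS last-contact date; the visit-only note, if followed literally, would bias OS downward

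*SAP*

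**What the plan says.** SAP Appendix 1.3, under the heading on date of last contact for overall survival, derives the date for patients not known to have died at the data cutoff, "using the latest complete date (non-imputed) among the following". The sources include:

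- "Last date of contact where 'Patient Remains in Follow-up' collected on the 'Survival Follow-up' eCRF", with the instruction "do not use date of survival follow-up assessment unless status is alive";
- "Start and end dates of follow-up anti-cancer therapies";
- adverse event start and end dates;
- study drug start and end dates.

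A note follows. Its first bullet has two sentences: "Only dates associated with patient visits or actual examinations of the patient should be used", and then "Dates associated with a technical operation unrelated to patient status (eg, the date a blood sample was processed) should not be used". Its second bullet bars assessment dates after the cutoff.

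Three other places bear on the same date:

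- SAP 3.2: patients without a documented death "will be censored at the date last known to be alive".
- SAP 8.2.3.3, efficacy overview table: OS is censored at the date of last contact, with a reference to Appendix 1.3.
- SAP 8.2.1, duration of OS follow-up: for patients who have not died, follow-up ends at the last visit at which they were known to be alive.

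**The concern.** Read literally, the note's first sentence removes dates that the list above it tells the programmer to use. A survival follow-up contact need not be a visit. Protocol 7.1 dispenses a month of BBI608 at a time from cycle 2, so a last-dose date is often not a clinic date. Adverse events are reported by patients (Protocol 8.1.2), so an onset date need not be one either. The same holds for therapy started elsewhere after the study.

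The restriction would act on one side only. The last-contact rule applies to patients not known to have died, while SAP 3.2 counts a death at its date with no visit requirement. Under the strict rule, a patient known to be alive well after the end-of-study visit leaves the risk set at that visit, but a patient who dies at the same later time stays in it until death. That is informative censoring, and it pulls the OS estimate down. The reverse Kaplan-Meier follow-up time in SAP 8.2.1 would be understated as well if it used the same visit-based date.

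**Working it through.** **Step 1: the texts side by side.**

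| Place in the SAP | Date used for a survivor | Limited to visits? |
|---|---|---|
| Appendix 1.3, list | latest complete date among the listed sources, including survival contacts with status alive | no |
| Appendix 1.3, note, first sentence | visit or actual examination | yes |
| 3.2 | date last known alive | no |
| 8.2.3.3, overview table | date of last contact | no |
| 8.2.1, OS follow-up duration | last visit known alive | yes |

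No sentence says which rule prevails.

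**Step 2: when visits could end.** Protocol 4.6 expects most patients to be treated for 4 to 16 weeks, and Protocol 5.5 follows patients for at least 30 days after the last dose. In months of 30.44 days:

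- shortest: (28 + 30)/30.44 = 1.9, taken as 2;
- longest: (112 + 30)/30.44 = 4.7.

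**Step 3: effect of the strict reading.** The documents give no OS median, event count or cutoff, so there is no planned figure to reproduce and these inputs are assumed. Survival is exponential with a true median of 8 months, S(t) = 0.5^(t/8). All patients are followed to a common time c. Every survivor at c is censored at v, and deaths count at their true times.

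Up to v the Kaplan-Meier curve equals S(t). After v the risk set holds only patients who die before c, so

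KM(t) = S(v) × [S(t) − S(c)] / [S(v) − S(c)].

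Setting KM = 0.5 gives S(t) = S(c) + 0.5 × [1 − S(c)/S(v)].

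Example with v = 2 and c = 18:

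- S(v) = 0.8409 and S(c) = 0.2102.
- S(t) = 0.2102 + 0.5 × (1 − 0.2500) = 0.5852, so t = −8 × log2(0.5852) = 6.18 months.
- At 12 months, 0.8409 × (0.3536 − 0.2102)/0.6307 = 0.191, against a true 0.354.

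For v from 2 to 4.7:

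| Cutoff c (months) | Alive at c | Median read (true 8.0) | 12-month survival read (true 35%) |
|---|---|---|---|
| 18 | 21.0% | 6.18 to 6.85 | 19 to 21% |
| 24 | 12.5% | 6.89 to 7.30 | 27 to 28% |
| 36 | 4.4% | 7.59 to 7.75 | 33% |
| 48 | 1.6% | 7.85 to 7.91 | 34 to 35% |

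**Step 4: check with staggered entry.** A simulation of 1,000 trials used 50 patients per arm (the approximate number per arm in SAP 4.3) and treatment of 4 to 16 weeks plus 30 days. It assumed uniform accrual over 24 months, a survival contact about every 3 months, and a cutoff 3, 12 or 24 months after the last patient.

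| True median (months) | List reading | Strict note reading |
|---|---|---|
| 6 | 5.8 to 5.9 | 5.0 to 5.9 |
| 9 | 8.7 to 8.8 | 6.4 to 8.4 |
| 12 | 11.3 to 11.7 | 7.3 to 10.3 |

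The largest gap is 7.3 against 11.3 months (true median 12, cutoff at 3 months). There is none for a true median of 6 with a cutoff at 24 months (5.9 under both readings). The direction matches step 3, and the effect shrinks as fewer patients remain alive at the cutoff.

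**The case against.** A reader might infer that the SAP does censor survivors at their last visit and that its OS estimate is therefore biased. The documents do not establish that:

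- The list names the survival follow-up form and says when its date may be used. That specific instruction would have little purpose if the note overrode it.
- The note's second sentence suggests that its target is administrative dates such as sample processing, not contacts with the patient.
- SAP 3.2 and the table in 8.2.3.3 fit the list.
- Neither document says whether survival contacts are made by telephone or in clinic. Some may be visits and would satisfy both rules.

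The size can also be overstated. Protocol 4.6 speaks only of most patients. Treatment continues until progression or toxicity (Protocol 4.1), tumour assessment runs up to one year (Protocol 5.4), and SAP 7.1 provides for patients still on treatment at the cutoff, so long survivors are the likeliest to have later visits. The cutoff is not stated. Because the SAP cites a protocol amendment of October 2014 and its own third amendment is dated September 2020, long follow-up is plausible.

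All of this stands, and it makes the list the more natural reading. It does not remove the conflict. The note comes after the list and says only. Its companion bullet on the cutoff is plainly a binding filter, so the first bullet can be read as one too. SAP 8.2.1 also uses a visit-based date. A programmer could follow either rule and cite the SAP for it.

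**Conclusion.** The point holds as an unresolved contradiction in a stated censoring rule, with a known direction of bias under one of its two readings. It does not show that the plan has adopted a biased rule.

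Under the strict reading OS is biased downward. With an assumed 8-month exponential median and survivors' last visit at 2 to 4.7 months, the loss in the median runs from about 1.1 to 1.8 months at an 18-month cutoff (8.0 less 6.85 and 6.18) to about 0.1 month at 48 months (8.0 less 7.91 and 7.85). Those figures assume that no survivor has a later visit, so they lie at the unfavourable end for each cutoff.

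OS is a descriptive secondary endpoint, SAP 4.1 states that nothing is tested, and no decision rests on it. The severity is modest, but the medians and intervals will be reported by arm and sub-cohort, so the rule should be settled before the analysis.

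**What to change.** In SAP Appendix 1.3, delete or reword the first sentence of the note and keep its second sentence on technical-operation dates. Suggested wording: any listed date on which the patient was known to be alive is used, including a survival follow-up contact with status alive and no visit.

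In SAP 8.2.1, end OS follow-up for patients who have not died at the date last known alive, in place of the visit-based date, so that it agrees with 3.2 and 8.2.3.3.

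The cost is two sentences in the SAP. No new data are needed.
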